12.1.3 Inclusion and Exclusion Criteria

Failed inclusion and exclusion criteria for randomized patients will be presented in a data listing.

12.2 Demographic and Baseline Characteristics

12.2.1 Demographics

Baseline data will be summarized for continuous and categorical variables as applicable.

The following demographic and baseline characteristics will be summarized:

- Sex (female, male)
- Race (White, Black or African American, Asian, American Indian or Alaska Native, Native Hawaiian or Pacific Islander, Other)
- Ethnicity (Hispanic or Latino, not Hispanic or Latino)
- Age (years) at Baseline, as continuous variable and Age groups (6 to 11 years; 12 to <18 years, ≥ 18 years)
- Height at Baseline (m)
- Weight at Baseline (kg)
- Body mass index at Baseline (kg/m²) defined as Weight (kg)/[Height (m)]²
- Women of child-bearing potential
- Patients with/without concomitant sleep disorders (or sleep disorder symptoms) that could
 potentially contribute to EDS beyond the EDS associated with PWS. Medical terms that
 are specifically used to describe EDS (e.g., hypersomnia, hypersomnolence, sleepiness,
 etc.) will not be used to infer a concomitant sleep disorder or sleep disorder symptom as
 EDS is required for study entry.

At the time of the Double-Blind Treatment Phase database lock, the above information will be tabulated by treatment arm, active arms pooled and overall, using the mITT, PK and the Double-Blind safety populations. At the time of OLE Phase database lock, the above information will be tabulated using the Open-Label safety population.

Data will not be re-collected at entry to the OLE Phase but will be reported for the subset of patients who enter the OLE Phase.

Demographic information will be presented in a data listing. No statistical testing will be performed on the demographic data.

12.2.2 Medical History

A complete medical history will be obtained at Screening to ensure patients qualify for the study and will be updated at the Baseline visit if needed.

Medical history will be summarized for all patients in the safety populations. Medical history data will be coded using the Medical Dictionary for Regulatory Activities (MedDRA). The version used will be included in the tables and listings footnotes and summarized by system organ class and preferred term. No inferential testing will be performed in this section. Medical history data will be presented in a data listing.

12.2.3 Seizure History

Seizure history will be obtained at Screening and will be updated at the Baseline visit if needed.

For all patients in the safety population, in those patients with a history of a seizure disorder, the following aspects of their seizure history will be summarized.

- Has there been any change in seizure activity in the past 3 months (prior to the study)?
- Type of seizure disorder
- Average weekly seizure frequency
- Average seizure duration in seconds

No inferential testing will be performed in this section. Seizure history data will be presented in a data listing.

12.2.4 Prader-Willi Syndrome History

Confirmation of a patient's diagnosis of PWS will be obtained via review of the patient's medical records. Age at diagnosis of PWS and the type of PWS will be tabulated.

- Age at diagnosis of PWS (years) = (date of diagnosis date of birth)/365.25
- Type of PWS

The date of diagnosis of PWS and the type of PWS will be presented in a data listing. If the date of diagnosis is partial, the date will be imputed as:

- If only the day is missing it will be imputed as the 15th day of the month
- If the day and month are missing, they will be imputed as 15th of July

12.3 Treatments

12.3.1 Prior, Concomitant and Prohibited Medications

Medications that stop prior to the first dose of study drug will be classified as prior medications. Medications that start on or after the first dose of study drug will be classified as concomitant. If a medication starts before the first dose of study drug and stops on or after the first dose of study drug (or is ongoing), then the medication will be classified as both prior and concomitant.

Medications will be categorized by medication group and subgroup according to World Health Organization (WHO) drug dictionary (the version used will be included in the tables and listings footnotes).

Missing or partial medication start/stop date will be imputed as described in Appendix 2. A conservative approach will be used when flagging medications.

Prior and concomitant medications will be summarized by preferred name and medication class. Frequency count and percentage of patients using each medication along with the number and percentage of patients using at least one medication within each medication and medication class will be presented. All medications will be listed.

For patients who opt to continue in the OLE Phase of the study, only medications starting strictly before the first dose in the OLE Phase will be summarized for the Double-Blind Treatment Phase, and any medications that started on or after the first dose of treatment in the OLE Phase and up to 30 days after the last dose of treatment in the Double-Blind Treatment Phase will be included in a

separate listing (for the OLE Phase reporting); these medications will be included in the OLE Phase summaries.

12.3.1.1 Prohibited and Restricted Concomitant Medications

The use of medications that may prolong the QT interval is not permitted in the study.

Use of opiates is not permitted in the study.

Except for diazoxide choline, use of investigational drugs (i.e., drugs that are not FDA-approved for any indication) are prohibited.

The use of strong CYP2D6 inhibitors or strong CYP3A4 inducers is not permitted during the Double-Blind Treatment Phase of the study, and if being used, should be discontinued at Screening; washout of 5 half-lives or 1 week (whichever is longer) of these medications is required prior to enrollment and initiating study drug. These medications (Appendix 3) are allowed during the OLE Phase of the study, but adjustment of the dose of pitolisant may be required.

Pitolisant increases the levels of histamine in the brain; therefore, centrally acting histamine 1 (H₁) receptor antagonists that cross the blood-brain barrier may reduce the effectiveness of pitolisant. Concomitant use of centrally acting H₁ receptor antagonists is not permitted during the Double-Blind Treatment Phase of the study (requires a washout of 5 half-lives or 14 days, whichever is longer, prior to randomization). Although not prohibited during the OLE Phase of the study, use of these medications should be avoided and, if needed, will require consultation with the Medical Monitor.

Prohibited medications taken in the study will be reported and summarized as part of the protocol deviations summary/listing.

12.3.2 Extent of Study Drug Exposure

Descriptive statistics will be provided by treatment group for the Double-Blind Treatment Phase analyses and by treatment group received, active arms pooled, and overall, during the Double-Blind Treatment Phase and overall, for the OLE Phase analyses.

12.3.2.1 Double-Blind Treatment Phase

The duration of exposure to study drug, number of days with intake of study drug and compliance (during the stable dose period) with study drug dosing will be summarized for the Double-Blind safety population. In addition, the number of tablets taken (i.e., returned – dispensed) will be listed for the titration phase and the stable dose phase in the Double-Blind Treatment Phase.

Study drug accountability including bottle number and number of dispensed and returned tablets will be listed. Study drug not returned will be assumed to have been taken.

Percentage of patients meeting study drug compliance during the stable-dose period will be presented in the following categories: <80%, $\ge80\%$ to $\le120\%$, and >120%. Major non-compliance is defined as compliance <80% or compliance >120%.

Duration of exposure: Date of last dose in the Double-Blind Treatment Phase – date of first dose in the Double-Blind Treatment Phase + 1

Number of days with at least one dose (tablet) taken: Duration of exposure in the Double-Blind Treatment Phase – number of days with missed doses in the Double-Blind Treatment Phase

Study drug compliance (stable-dose period): The start date of the stable dose period is the date of Visit 3 (Day 22) and the end of the stable dose period is the last dose date in the Double-Blind Treatment Phase; during that period patients ages 6 to <12 years should take 4 tablets daily, patients ages 12 to <18 years should take 6 tablets daily, and patients ages \ge 18 years should take 2 tablets daily; i.e., compliance is the number of tablets taken during that period (i.e., sum of the tablets dispensed minus the sum of the tablets returned) divided by (x times the number of days in the period [date of last dose – dispensed date at Visit 3 +1]), where x is 4 for patients ages 6 to <12 years, 6 for patients ages 12 to <18 years and 2 for patients ages \ge 18 years.

The data from the dose-escalation period was not included in the derivation of the compliance as the dates when the patient dose-escalated to the next dose level is not collected in the eCRF and the number of tablets to be taken at each dose level is different.

12.3.2.2 OLE Phase

The duration of exposure to study drug will be summarized for the Open-Label safety population. Study drug accountability and number of dispensed and returned tablets will be listed.

Duration of exposure: Date of first dose in the OLE Phase – date of last dose in the OLE Phase + 1 In addition, the following measures of changes in planned dose will be summarized for the Open-Label safety population:

- Planned average daily dose: sum of the daily dose x duration of intake (end date minus start date + 1) divided by the duration of exposure
- Number and percentage of patients with at least one dose adjustment per reason (AE, dosing error, rechallenge, insufficient effectiveness, change in dose assignment criteria and other)
- Number and percentage of patients with one dose adjustment, with two dose adjustments and with >2 dose adjustments due to any reason
- Number and percentage of patients with one dose adjustment, with two dose adjustments and with >2 dose adjustments due to AE
- Number and percentage of patients with one dose adjustment, with two dose adjustments and with >2 dose adjustments due to rechallenge
- Number and percentage of patients with one dose adjustment, with two dose adjustments and with >2 dose adjustments due to insufficient effectiveness

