1.3.2. Dosing (OLE Phase After Implementation of Protocol Amendment 6)

The dosing regimens (Table 9) were selected based on:

- Efficacy signals that were observed for the higher dose pitolisant treatment group in the completed Double-Blind Treatment Phase of this study, suggesting a target for dosing of approximately mg/kg.
- Population PK simulations:
 - Area under the curve during a dosing interval at steady state (AUCtau) and maximum observed concentration (Cmax) in patients with PWS receiving the dosing regimens were similar to those in patients with narcolepsy receiving the doses included in the FDA-approved prescribing information for WAKIX (pitolisant).
 - The estimated risk of QT interval prolongation in patients with PWS using the dosing regimens described in Table 9 is consistent with the risk described in patients with narcolepsy in the FDA-approved prescribing information for WAKIX (pitolisant).
- Safety data:
 - Pitolisant is well tolerated in adult and pediatric patients with narcolepsy and in ongoing clinical development programs at doses up to 35.6 mg once daily.
 - Pitolisant is well tolerated in adult and pediatric patients with PWS at doses up to 35.6 mg in the Double-Blind Treatment Phase of this study and up to mg in studies HBS-101-CL-003 and HBS-101-CL-004.

- The safety/tolerability profile of pitolisant in pediatric patients is generally consistent with the established safety/tolerability profile in adult patients.
- No dose-related adverse effects were identified in the pooled narcolepsy New Drug Application (NDA) safety population of 1513 patients who received pitolisant 17.8 mg or 35.6 mg once daily for a mean of 33 weeks.

During the OLE Phase, pitolisant dose can be adjusted (higher or lower) based on Investigator discretion (Section 3.1.5.2).

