3.1.5.2. Open-Label Extension Phase

Adjustments in pitolisant dose are permitted in the OLE Phase.

Prior to implementation of Amendment 6, pitolisant doses could be adjusted (higher or lower) in 4.45 mg increments based on Investigator assessment of clinical response, tolerability and/or patient age.

After implementation of Amendment 6, pitolisant dose may be adjusted (higher or lower) based on Investigator discretion in consultation with the Medical Monitor up to the maximum daily dose allowed (Table 9).

In the event a patient develops moderate hepatic impairment (Child-Pugh B) or moderate or severe renal impairment during the study, the dose of pitolisant may need to be decreased by the Investigator in consultation with the Medical Monitor. Patients who develop either end-stage renal disease (estimated glomerular filtration rate [eGFR] of <15 mL/minute/1.73 m²) or severe hepatic impairment (Child-Pugh C) must be withdrawn from the study (Section 4.4.1).

If a patient began taking a strong CYP2D6 inhibitor during the OLE Phase, prior to implementation of Amendment 6, pitolisant dose was to be reduced by one half of the maximum age-based dose (Table 8).

If a patient begins taking a

strong CYP3A4 inducer during the OLE Phase, pitolisant dose may be increased up to the maximum permitted daily dose based on the patient's age (prior to implementation of Amendment 6)

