6.0 Introduction

This SAP should be read in conjunction with the study protocol Amendment 5, Version 6.0 (dated 13 December 2021) and case report form (CRF) Version 4.0 (dated 28 April 2022). Any further changes to the protocol or CRF may necessitate updates to the SAP.

Final approval of the SAP by Harmony Biosciences and by PRA will occur prior to unblinding the Double-Blind Treatment Phase of the study.

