9.6 Double-Blind and OLE Analyses Reporting

The data collected for the Double-Blind Treatment Phase and the OLE Phase are included in the same database.

A CSR will be written at the end of the Double-Blind Treatment Phase and another one at the end of the OLE Phase. The date of first dose in the OLE Phase will be used to determine if the patient entered the OLE Phase.

Double-Blind Treatment Phase:

For reporting of the Double-Blind Treatment Phase analyses, a data cut-off will be applied to the datasets and only data related to the Double-Blind Treatment Phase will be reported, i.e.,

- Baseline and baseline characteristics
- Visits performed in the Double-Blind Treatment Phase, up to and including Visit 5 (Week 11) for patients who entered the OLE Phase and through the safety follow-up visits for patients who opt out of the OLE Phase
- For patients who entered the OLE Phase, any AE or medication that started up to and excluding the first dose of study drug in the OLE Phase.
- For patients who opt out of the OLE Phase, all AEs and medications reported through the final 30-day safety follow-up telephone contact will be reported as part of the Double-Blind Treatment Phase

The date of first dose in the OLE Phase will be kept in the datasets to determine if the patient has entered the OLE Phase.

OLE Phase:

For reporting of the OLE analyses, no data cut-off will be applied to the datasets but only data related to the OLE Phase will be reported, i.e.,

- Demographics and baseline characteristics for patients who received at least one dose of study drug within the OLE Phase
- Baseline of the safety and efficacy data (section 9.3)
- Safety and effectiveness reported during the OLE Phase
- AE and concomitant medications started on or after the 1st dose of OLE study drug intake

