12.5 PK Analyses

Plasma concentration-time data of pitolisant and BP1.3484 will be summarized using descriptive statistics by age group (6 to <12 years; 12 to <18 years, ≥18 years), treatment group, and scheduled sampling interval. The following summary statistics will be included for plasma concentration-time data: mean, SD, coefficient of variation (CV%), geometric mean, geometric SD, median, minimum, and maximum.

Plasma concentration-time profiles of pitolisant and BP1.3484 will be plotted on semi-log and linear scales for each individual patient as spaghetti plots by age group (6 to <12 years; 12 to <18 years, ≥18 years) and treatment group using actual collection times. For ease of presentation, mean plasma concentration-time data of pitolisant and BP1.3484 will be plotted separately by midpoint (on hour scale) for the planned interval on both linear and semi-logarithmic scales. Plasma PK concentrations of pitolisant and BP1.3484 for each individual will be reported to the precision of the raw data in listing presentations. In addition, concentration-time profiles for each analyte will be plotted by patient.

Values reported as below the lower limit of quantification (LLOQ) or below the limit of quantification (BLQ) i.e., reported as <LLOQ (BLQ) will be imputed to be 0.

If data allow, the following steady-state PK parameters will be calculated for each analyte as listed in Table 12.

Table 12: PK Parameters

Parameter	Description	PK Analysis Notes	Analyte	SAS Programming Notes
C _{max}	Maximum plasma concentration. Observed peak analyte concentration obtained directly from the experimental data without interpolation, expressed in concentration units.		Pitolisant and BP1.3484	Cmax from WinNonLin software (WNL) version 8.1.1 or later.
T _{max}	Time to reach C _{max} in plasma. The time to reach maximum concentration is obtained directly from the experimental data without interpolation and expressed in time units.		Pitolisant and BP1.3484	Tmax from WNL
AUC _(0-T)	Area under the concentration-time curve from time 0 (dosing) to the time of the last quantifiable concentration observed, without interpolation or extrapolation, using trapezoidal summation. AUC _(0-T) is expressed in concentration*time units.	Calculated by the linear up/log down method in WNL	Pitolisant and BP1.3484	AUClast from WNL

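### The SAP's open-label exposure formula has its two dates reversed, so durations come out negative and the average daily dose built on them is wrong

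*SAP*

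**What the plan says.** SAP 12.3.2.2 gives OLE duration of exposure as "Date of first dose in the OLE Phase – date of last dose in the OLE Phase + 1". The next definition, planned average daily dose, sums daily dose times duration of intake, using "end date minus start date + 1) divided by the duration of exposure". Its numerator therefore takes the later date first, while its denominator is the reversed quantity.

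For the double-blind phase, SAP 12.3.2.1 uses "Date of last dose in the Double-Blind Treatment Phase – date of first dose in the Double-Blind Treatment Phase + 1". SAP 9.4 only imputes an unknown last-dose date. No section that can be read gives a different OLE formula.

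On PK, SAP 12.5 states that values "reported as <LLOQ (BLQ) will be imputed to be 0". The same section asks for the geometric mean, geometric SD and semi-log plots of those concentrations, with no rule for zeros. Protocol 9.4.4 plans semi-log plots too, but lists geometric statistics for PK parameters only, not for concentrations. SAP 6.1 does not list the addition among its changes from the protocol.

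Two smaller items sit nearby. SAP Table 12 labels the trough concentration with Days 22, 50 and 77, whereas SAP Table 6 schedules a pre-dose sample only at Visit 4 (Day 50). SAP 12.3.2.1 describes tablets taken, for a listing, as returned minus dispensed, then uses dispensed minus returned for compliance.

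**The concern.** The OLE duration is an operative derivation rule. If programmed as written, it gives a wrong duration for every patient with more than one day of open-label treatment, and the error passes into planned average daily dose. These are the exposure measures the SAP specifies for the Open-Label safety population, and long-term safety and effectiveness is a stated secondary objective. Average dose is informative here because doses can vary between patients: Protocol 3.1.5.2 says "Adjustments in pitolisant dose are permitted in the OLE Phase", and Amendment 6 changed OLE dosing.

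The BLQ rule raises a narrower problem. One zero in a summary cell makes the geometric mean 0 or not calculable and leaves the geometric SD undefined, and a zero cannot be drawn on a log axis.

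**Working it through.** **Inputs.** Formulas: SAP 12.3.2.1 and 12.3.2.2. First open-label dose on Day 78: SAP 8.1 and Protocol 3.1.4. Visit 9 on Day 369, used as an illustrative last-dose day: Protocol 3.1.4. OLE doses by week: SAP Table 2. The documents state no OLE exposure figure, so there is none to reproduce.

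**Check of the convention.** The double-blind formula applied to Days 1 to 77 gives 77 − 1 + 1 = 77 days = 11 weeks, which matches the planned phase length.

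**OLE duration.** Let D = last − first + 1. The written formula is W = first − last + 1. Since first − last = 1 − D, W = 2 − D.

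**Average daily dose.** With total planned dose T, the correct value is T/D and the written value is T/(2 − D). Their ratio is D/(2 − D).

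| Days | Correct D | As written, 2 − D | Dose factor D/(2 − D) |
|---|---|---|---|
| 78–78 | 1 | 1 | 1 |
| 78–79 | 2 | 0 | undefined |
| 78–84 | 7 | −5 | −1.40 |
| 78–98 | 21 | −19 | −1.105 |
| 78–369 | 292 | −290 | −1.007 |

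Taking absolute values leaves duration at D − 2 for any span over two days. Average dose is then too high by D/(D − 2): 40% at 7 days, 10.5% at 21 days, 0.7% at 292 days.

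**Illustration in mg**, assuming SAP Table 2 dosing with no adjustments:

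- Adults, Days 78–98: T = 7×8.9 + 7×17.8 + 7×35.6 = 436.1 mg. Correct 436.1/21 = 20.77; as written 436.1/(−19) = −22.95.
- Adults, Days 78–369: T = 7×8.9 + 7×17.8 + 278×35.6 = 10083.7 mg. Correct 10083.7/292 = 34.53; as written 10083.7/(−290) = −34.77.
- Adolescents, Days 78–369: T = 7×8.9 + 7×17.8 + 278×26.7 = 7609.5 mg. Correct 26.06; as written −26.24.
- Children, Days 78–369: T = 7×4.45 + 7×8.9 + 278×17.8 = 5041.85 mg. Correct 17.27; as written −17.39.

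**BLQ.** Take the invented values 0, 10, 20 and 40. The geometric mean is (0×10×20×40)^(1/4) = 0, and the geometric SD is undefined because log(0) is undefined. Without the zero they are 20 and 2.0.

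**Trough label.** Samples at Visits 3 and 5 are scheduled after the morning dose, so two of the three named days have no scheduled pre-dose draw. Protocol 6.6.1.2 allows the Visit 4 series to be moved as late as Visit 5, so a Day 77 pre-dose value is possible in some patients.

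**The case against.** The strongest reply is that this is a transposition of two dates and not a chosen method. The intended order appears in the double-blind formula and in the numerator of the average dose. A negative duration or daily dose could not pass as a result, so a programmer would probably notice. The outputs are descriptive, and no p-values are planned for the OLE. The mg figures assume unadjusted dosing, which the protocol does not require.

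Most of this is fair and limits the weight of the point. It does not make the formula right. Noticing the sign is not the same as correcting the rule: an absolute-value patch looks plausible and leaves an error that is hard to see in long-term patients. The mg figures are illustrations only; the factor D/(2 − D) needs no dosing assumption. The error also does not rise steadily toward shorter stays: a one-day patient has none, and it is worst just around two days.

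The BLQ point is conditional. Placebo patients are excluded from the PK population (SAP 10.4), so it arises only if an active-arm sample is BLQ, and the documents give neither a quantification limit nor a BLQ frequency. Arithmetic mean, median and range are still reported. The trough label is largely protected because Table 12 defines the value as taken just before dosing and calculates parameters only where data permit. The tablet sign affects one listing, beside a correct compliance formula.

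**Conclusion.** The OLE exposure formula is wrong as written. It equals 2 minus the true duration, and it carries into planned average daily dose by the factor D/(2 − D). This follows from the text alone and rests on no assumption; only the mg illustrations assume unadjusted SAP Table 2 dosing and the stated last-dose days. It should be corrected, but its reach is descriptive: OLE exposure summaries only, with no efficacy analysis or hypothesis test affected.

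The BLQ conflict is real but secondary, and no size is claimed for it. The trough label and the tablet sign are minor wording corrections.

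**What to change.** 1. In SAP 12.3.2.2, define OLE duration of exposure as last OLE dose date − first OLE dose date + 1, matching 12.3.2.1. Planned average daily dose then needs no further change.
2. In SAP 12.5, keep BLQ = 0 for arithmetic summaries and linear plots. For log-scale output, report the BLQ count and show geometric statistics as not calculable in affected cells, or state a positive substitution value.
3. Minor: tie the trough entry in Table 12 to the actual pre-dose draw (scheduled on Day 50, or wherever the Visit 4 series is moved), and list tablets taken as dispensed − returned.

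These are text edits, with no new data and no protocol or CRF change. There is a natural place for the first: SAP 9.6 says "A CSR will be written at the end of the Double-Blind Treatment Phase and another one at the end of the OLE Phase", and SAP 6.0, which is written to Amendment 5, says "Any further changes to the protocol or CRF may necessitate updates to the SAP". The PK and tablet items concern a phase that Protocol 1.3.2 already treats as finished ("in the completed Double-Blind Treatment Phase of this study"), so they may have to be documented in the clinical study report instead.
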